In addition to establishing the benefits of exercise training in people with 'watch and wait' CLL, this study provides a unique methodological model to investigate the effects of exercise on neoplastic activity in humans. Given that CLL tumour cells are highly abundant in peripheral blood (>5000 cells/ul) and thus easily and relatively non-invasively accessible, and the absence of confounding therapies (e.g. anti-cancer therapy), that are typical of other cancer diagnoses, people with 'watch and wait' CLL provide a unique model to prospectively assess the short-term effects of exercise training on tumour cell mass and activity *in vivo*, and in doing so conduct mechanistic investigations to discover how regular exercise averts tumour growth in humans. A number of anti-tumour mechanisms of exercise have been proposed, including immune function, inflammation, adipose tissue and metabolic hormones (McTiernan, 2008), which will be explored as secondary outcome measures in our study herein.

Accordingly, this study aims to confirm the safety and acceptability of an exercise programme in people with 'watch and wait' CLL, as well as preliminarily explore the effects of exercise training (pre-intervention to post-intervention) on tumour cell mass (CLL tumour cell frequency) in peripheral blood. The aforementioned data will be used as preliminary data for a power calculation, for a future larger randomised control trial. Additionally, this study will enable preliminary assessment of changes (pre-intervention to post-intervention) to a wide range of health outcomes in people with 'watch and wait' CLL, including cardiorespiratory fitness, strength, body composition, free-living physical activity levels, and wellbeing and physical function indices. Finally, this study will enable preliminary assessment of the changes (pre-intervention to post-intervention) to the potential anti-tumour mechanisms of exercise including immune function, inflammation, adipose tissue and metabolic hormones.

The hypotheses of this pilot study are as follows:

- Exercise will be safe and acceptable in people with 'watch and wait' CLL.
- Exercise will reduce the frequency of CLL tumour cells in the peripheral blood of people with 'watch and wait' CLL.
- Exercise will improve the cardiorespiratory fitness and the health and wellbeing of people with 'watch and wait' CLL.

Aims and outcomes

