The present trial will investigate the safety and acceptability of a 16-week home-based, progressive, exercise training intervention.

Primary objective:

1. Investigate the safety and acceptability of an exercise training intervention, in physically inactive people, with 'watch and wait' CLL.

Outcome measures, collected throughout the trial period:

- Safety (incidence and severity of adverse events)
- Uptake (proportion of people approached who attend screening, proportion of people who attend screening that are deemed eligible)
- Adherence (proportion of exercise sessions prescribed that are actually completed)
- Compliance (prescribed vs. actual aerobic exercise performed per exercise session)
- Retention (the proportion of participants who complete baseline measures that also complete follow-up measures)

Secondary objective:

1. Investigate the effect of an exercise training intervention on CLL disease activity, immune markers, overall fitness, health and wellbeing in physically inactive people, with 'watch and wait' CLL.

Outcome measures, collected pre- and post-trial period:

- Frequency of CLL cells in peripheral blood measured by flow cytometry
- Immune competency (e.g. phenotypic and functional analyses of PBMCs, differential blood count, viral infection history, immunoglobulins, complement proteins)
- Basal inflammation (e.g. cytokines)
- Metabolic factors and hormone levels (e.g. glucose, insulin, growth factors)
- Clonality of tumour cells (e.g., PCR).
- Genetic and epigenetic features of tumour and immune cells.
- Cardiorespiratory fitness (predicted, or VO_{2MAX})
- Body strength (measured by 1-rep max resistance exercises)
- Body composition (height, weight, waist and hip circumference, fat mass, lean mass)
- Wellbeing indices (stress, fatigue, sleep, quality of life, frailty, motivation, self-efficacy)
- Free-living physical activity levels via wearable technology (e.g., duration, intensity, frequency, energy expenditure and sedentary time)
- Physical function (e.g., flexibility, sit-to-stand test)
- Resting blood pressure, and heart rate
- Left ventricular (LV) function (volumes; ejection fraction; strain; diastolic function)
- Comparison of LV manual measures with artificial intelligence

Trial design

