This is a single-centre, double armed, randomised-controlled, phase I pilot trial, designed to evaluate the safety and acceptability of an incremental, multi-modal, 16-week exercise training intervention. The intervention will be observed by a member of the Research Team via a video communication platform in physically inactive people with 'watch and wait' CLL, compared to standard care, which comprises routine clinical monitoring.

Participant eligibility criteria

The following inclusion criteria define people who are eligible for the trial:

- Males and females with a working diagnosis of: Chronic lymphocytic leukaemia. Defined by iwCLL guidelines as the presence of 5000 B cells per µL of peripheral blood, sustained for at least 3 months and confirmed by the blood smear, immunophenotype and in some cases genetic features of lymphoid cells (Hallek et al., 2018a).
- Age > 18 years old.
- Asymptomatic early stage disease monitored without anti-CLL treatment.
- Physically inactive (defined by World Health Organisation as 'An insufficient physical activity level to meet present physical activity recommendations'. Current physical activity guidelines for adults are at least 150-300 minutes of moderate-intensity aerobic physical activity, or at least 75-150 minutes of vigorous-intensity aerobic physical activity, or an equivalent combination of both throughout the week (Bull et al., 2020)).
- Access to an appropriate electronic device (e.g. laptop, tablet or smart phone) with an appropriate wireless internet connection (and data allowance if relevant) capable of streaming video.
- All participants will have completed the full appropriate vaccination schedule including seasonal influenza, pneumococcal and COVID-19.

Sub-groups will be excluded due to safety risks:

- World Health Organisation (WHO)/ Eastern Cooperative Oncology Group (ECOG) performance status >1
- Pregnancy
- Deemed unsafe to exercise according to the Physical Activity Readiness Questionnaire (PARQ)
- Any comorbidity that is likely to progress or be exacerbated over the course of the trial period (e.g. history of syncopal events, significant cardiac or respiratory events)
- Cognitive impairment deemed a risk by the healthcare team for participation in the trial (e.g. diagnosis of neurodegenerative disease)
- Unable to understand explanations and/or provide informed consent
- Any condition and/or behaviour that would pose undue personal risk or introduce bias into the trial

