The participant will be given resources and equipment (i.e., an instruction pack, food diary and activity monitor) for these measures at Visit 1 after informed consent has been obtained. This allows measures to be completed prior to Visit 2 which will be scheduled a minimum of 9 days after screening.

Dietary composition: Participants will be provided with a 3-day food diary and instructions that explain how best to record everything they eat (e.g. cooking method, brand) for two weekdays and one weekend day. The records will be analysed using Nutritics software with the primary aim of characterising any changes to dietary intake between measurement points.

Physical activity: Participants will be given a GENEActiv physical activity monitor at six measurement points throughout the study, initially at Visit 1 to enable measures of free living physical activity level to be taken prior to Visit 2 (pre trial period), a further four times during the trial period (weeks 2, 6, 10 and 14), to enable measures of free living physical activity level to be taken throughout, and a final time (post trial period) to enable measures to be taken after the trial (post trial period) has been completed. At each measurement point the participants will be asked to wear the monitor for 9 days (to capture at least 7 full days of wear) for measurement of free-living physical activity. The monitor is worn on the wrist and records acceleration and skin temperature continuously. No identifiable data is collected by the GENEActiv. Participants will be provided with instructions on how to use the monitor and these

instructions emphasise the importance of wearing the monitor continuously, the monitor is waterproof so can be worn during waterborne activities (e.g. showering/swimming). Data from complete days (>80% wear time) will be reported to examine any change in physical activity level between measurement points. The GENEActiv physical activity monitor will be loaned to the participant for the duration of measurement only. The devices are covered by the University of Bath insurance policy.

Visit 2 (Week 0)

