Lactate threshold will be determined by plotting a graph of power in watts (x-axis) against the blood lactate in mM (y-axis). The definition of the blood lactate threshold as the break-point where a curvilinear rise in lactate concentrations is observed when plotted against power will then be used to determine the power at which the lactate threshold occurred. Work rates corresponding to -5%, +5% and +15% of the lactate threshold will be calculated from the lactate – to – work rate relationship. These work rates will then be used as the exercise intensities during the training intervention.

Health and safety: Participants unable to comply with the exercise test, for example due to a health problem raised during the exercise test (e.g. abnormal blood pressure response) or serious discomfort exercising, will discontinue involvement in the study on safety grounds. Abnormal test results will be referred to a cardiologist who will provide follow-up care and advice on the participants continued involvement in the trial. The decision on whether to repeat baseline measures will be discussed with the trial management group; e.g. if follow-up care results in a considerable delay, there may be a need to repeat baseline measures prior to commencing further trial activities.

Randomisation

Eligible, consenting participants will be randomly allocated (1:1) to an exercise training intervention (ETI) or standard care control (CON) group. Randomisation will be performed using a web-based platform.

Trial period measurements

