A final important consideration for the research team when designing this study was the global COVID-19 pandemic. To minimise this risk, the exercise training intervention has been designed to be conducted in participants homes. Appropriate personal protective equipment (PPE) will be worn by the research team during Visit 1, Visit 2 and Visit 3 and the study will adopt the policies that the Trust is following and will begin recruiting when the host institution allows it.

COVID-19 Mitigation Strategies

Given safety and institutional directives with the COVID-19 pandemic in the UK, the research team will adhere to the below policies and procedures:

• Any team member displaying any COVID-19 symptoms (fever (38°C or higher), or sense of having a fever, cough, shortness of breath, muscle aches, sore throat, unexplained loss of taste or smell, diarrhoea, headache) must stay at home and organise for a COVID-19 test by contacting their GP.

- Participants and research team will use hand sanitiser on entry to the University
- The research team will be provided with appropriate PPE (apron, gloves and a face covering/face mask and face shield throughout study participant visits)
- The research team will change gloves and apron between every study participant contact
- The research team will thoroughly wash hands and forearms before and after the session (not just use hand sanitiser)
- All research equipment will be wiped down immediately with disinfectant spray and cloth between study participant sessions
- Where possible staff will be vaccinated, and lateral flow tests will be done.
- Only two members of the research team will enter the participants homes to deliver the exercise equipment, and they will be in the home for no more than 15 minutes.

Statistics and data analysis

Sample size

The aim is to recruit 40 participants. Assuming a recruitment rate of three to four people per month and 20% drop out, we estimate the target can be reached within a suitable time-frame of the funding period (16-18 months).

There is limited information available to enable a formal sample size calculation. This pilot trial will provide preliminary data to determine that a future RCT has promise and is not futile, and to perform a sample size calculation.

Statistical analysis plan

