Primary outcome measures do not lend themselves to statistical analysis. Safety will be reported as the incidence and severity of adverse events. Acceptability will be reported as proportions in terms of uptake, adherence, compliance and retention.

Secondary data will be tested for normality (e.g. Shapiro-Wilk) and in the event that some data are not normally distributed, the data will be log transformed. Descriptive statistics will be presented, and longitudinal differences and interaction effects will be identified using repeated-measures T-tests. These data will be used to inform sample size calculations in a future RCT. Incomplete data and missing values will be managed using an intention-to-treat approach with multiple imputation.

The project may utilise correlation analysis to establish whether any change in disease activity is associated to a number of mechanistic markers, and stepwise multiple regression will identify the extent to which a change in the mechanistic markers predict change in disease activity. Subgroup analysis may be performed, e.g. split to high vs. low responders or by presence of mediating variable(s) for further analysis.

Monitoring, audit and inspection

The University of Bath, as Sponsor, will monitor and conduct random audits on a selection of studies in its clinical research portfolio. Monitoring and auditing will be conducted in accordance with the Department of Health Research Governance Framework for Health & Social Care (April, 2005), and in accordance with the Sponsor's monitoring and audit policies and procedures.

Patient safety will be monitored on an ongoing basis by the research and healthcare team. A formal data monitoring committee will not be convened as this is a small single-centre pilot study. Instead, the research team will present an update on safety at quarterly trial management group meetings, together with the haematologist ([name] and/or [name]), the CI ([name]), and patient representative(s).

Ethical and regulatory considerations

Research Ethics Committee (REC) review

Before the start of the trial, approval will be sought from an NHS REC for the trial protocol, informed consent forms, participant information sheet and recruitment letter. Substantial amendments will require review by the NHS REC will not be implemented until the NHS REC grants favourable opinion.

Public and patient involvement

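### The secondary analysis aims to find interaction effects but names a paired t-test, which has no arm term, so the stated aim and the stated test contradict each other

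*Protocol*

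**What the plan says.** The Protocol's section on trial design describes a two-arm comparison of exercise training, "compared to standard care, which comprises routine clinical monitoring". Under Randomisation, participants are "randomly allocated (1:1) to an exercise training intervention (ETI) or standard care control (CON) group". The secondary objective, under Aims and outcomes, is to "Investigate the effect of an exercise training intervention on CLL disease activity, immune markers, overall fitness, health and wellbeing". One of the listed hypotheses is that "Exercise will reduce the frequency of CLL tumour cells in the peripheral blood". These are statements about an effect of exercise relative to usual care.

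The secondary outcomes are introduced as "Outcome measures, collected pre- and post-trial period", that is, Visit 2 and Visit 3. Free-living physical activity is the exception: participants wear the "GENEActiv physical activity monitor at six measurement points throughout the study".

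The only test named for these outcomes is in the statistical analysis plan subsection of Statistics and data analysis: "longitudinal differences and interaction effects will be identified using repeated-measures T-tests". The same subsection adds descriptive statistics, multiple imputation, correlation, stepwise regression and possible subgroup splits. It also says that the results will inform the sample size of a later trial.

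**The concern.** The sentence sets two tasks, change over time and interaction, and gives one tool for both. A paired t-test can do the first. It cannot do the second, because it has no arm in it. The other analyses in that subsection do not fill the gap: correlation and stepwise regression relate changes in markers to change in disease activity, and the subgroup splits are by response or by a mediating variable. None compares exercise with control.

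At stake is what the pilot can say about its secondary objective. Within-person change in the exercise arm mixes any exercise effect with whatever the controls also experience. Examples are familiarity with fitness and function tests repeated at Visit 3, regression to the mean, and drift in the CLL cell count over 16 weeks. The later trial needs a between-arm difference and its standard deviation for planning, and the named test provides neither.

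Silence in a protocol could be left to a separate analysis plan. Here the protocol itself fixes a method, so a valid analysis in another document would conflict with it.

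**Working it through.** **Inputs from the Protocol.** Two arms, 1:1 (Randomisation). "The aim is to recruit 40 participants", with 20% drop-out assumed (Sample size). That is 20 per arm if all are followed up, and 20 × 0.8 = 16 per arm after drop-out. The Protocol gives no alpha, effect size or SD for any secondary outcome, so there is no figure of its own to reproduce.

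**Assumptions.** Two-sided alpha 0.05; normally distributed change scores; all effects in units of the SD of change.

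**Step 1: what the interaction is.** Let D be a participant's Visit 3 value minus the Visit 2 value. The arm-by-time interaction is mean(D in exercise) − mean(D in control), and its test is an unpaired t-test on D. In a simulated data set with 16 per arm, the interaction F from the two-by-two mixed ANOVA was 1.441 and the squared unpaired t was also 1.441. The paired t-test instead asks whether mean(D) is zero in one set of people. That is a different hypothesis.

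**Step 2: paired tests run separately by arm, no exercise effect.** Both arms change by the same amount δ. Let p be the power of a paired t-test with n participants, from the noncentral t with n − 1 degrees of freedom and noncentrality δ√n. The arms are independent, so the probability of a significant result in exercise and not in control is p(1 − p).

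| Shared change δ | p, n = 16 | p(1 − p), n = 16 | p, n = 20 | p(1 − p), n = 20 |
|---|---|---|---|---|
| 0 | 0.050 | 0.048 | 0.050 | 0.048 |
| 0.2 | 0.117 | 0.103 | 0.136 | 0.118 |
| 0.3 | 0.203 | 0.162 | 0.247 | 0.186 |
| 0.5 | 0.465 | 0.249 | 0.565 | 0.246 |
| 0.75 | 0.801 | 0.160 | 0.889 | 0.099 |
| 1.0 | 0.962 | 0.037 | 0.989 | 0.011 |

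The function p(1 − p) cannot exceed 0.25. It comes close at δ = 0.5 because power is then near one half. In 40,000 simulated trials per setting, the unpaired test of change rejected in 4.8% to 5.2% at every shared change tried, from 0 to 1.0 SD.

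**Step 3: one paired test pooled over arms.** Take true changes of +0.5 SD in exercise and −0.5 SD in control, 16 per arm. The interaction is 1.0 SD, but the pooled mean change is zero. The pooled paired test rejected in about 3% of simulated trials and the unpaired test of change in 78%.

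**Step 4: efficiency of the alternatives.** With equal variances at the two visits and pre-post correlation r, the variance of the ANCOVA estimate relative to the change-score estimate is (1 − r²) / [2(1 − r)] = (1 + r)/2. This is 0.75 at r = 0.5 and 0.85 at r = 0.7. Both values of r are assumed.

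**The case against.** The strongest reply is that the sentence does commit to finding interaction effects. In a 1:1 two-arm trial this most naturally means arm by time, so a between-arm comparison is intended and only the name of the test is wrong. That stands. A reader might infer that the randomised comparison is never to be made, or that the randomisation is thrown away. The text does not support this; it shows an aim tied to a test that cannot deliver it.

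The protocol also does not say that the tests are run separately by arm, or that conclusions will rest on a change seen in exercise and not in control. That decision rule is inferred, and the table in the working depends on it. A reader might take 25% as the expected error rate. It is the mathematical ceiling, reached only near a shared change of 0.5 SD. The documents give no practice effect, drift or SD from which to choose a value.

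The point does not reach every secondary outcome. The comparison of manual and artificial-intelligence left ventricular measures is a method comparison with no randomised contrast.

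The descriptive statistics, if given by arm, would let someone compute the between-arm difference in change and, if the change scores are summarised, a planning SD. It therefore goes too far to say that the later trial could only be planned on within-arm change. But the protocol does not designate that difference as the estimate, and nothing else in it supplies an interval or a test for it.

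Finally, the pilot is exploratory and its primary outcomes are reported descriptively. This lowers the seriousness but does not remove the contradiction.

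**Conclusion.** The concern holds as a contradiction between aim and method: the protocol plans to identify interactions with a test that has no arm term, and names no other test that compares the arms. It applies to the secondary outcomes for which exercise is to be compared with usual care.

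If the plan is followed literally with separate tests by arm, and exercise has no effect, a result significant in exercise only occurs for about 5% of outcomes with no shared change. The rate is 10–12% at a shared change of 0.2 SD, 16–19% at 0.3 SD, at most 25% near 0.5 SD, 10–16% at 0.75 SD and 1–4% at 1.0 SD (16 to 20 per arm). A between-arm test gives 5% throughout. If the arms are pooled, a real difference in opposite directions can be missed almost entirely. These figures rest on the assumed alpha, normal change scores and the inferred decision rule; they illustrate the problem and do not forecast this trial's error rate.

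Safety, uptake, adherence, compliance and retention are untouched. The sentence should be corrected before analysis, but the primary purpose of the pilot does not depend on it.

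**What to change.** Replace the sentence with wording such as:

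*For each continuous secondary outcome measured at Visits 2 and 3, the effect estimate is the between-arm difference at Visit 3 adjusted for the Visit 2 value (ANCOVA), with 95% CI, in all randomised participants within the multiply imputed data; within-arm changes are descriptive. Free-living physical activity (six time points) is analysed with a mixed model with arm, time and arm-by-time terms, adjusted for baseline.*

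Use the adjusted between-arm difference and its residual SD when planning the later trial. An unpaired comparison of change scores would also remove the error. ANCOVA is preferred because it uses baseline data already collected and is at least as precise under the conditions in the working. The manual versus artificial-intelligence comparison of left ventricular measures is outside this change.

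The cost is an amendment of wording. No new data, visits or participants are needed.

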IPAQ	International Physical Activity Questionnaire
iwCLL	International Workshop on Chronic Lymphocytic Leukaemia
LV	Left Ventricular
METs	Metabolic Equivalents
PARQ	Physical Activity Readiness Questionnaire
PBMC	Peripheral Blood Mononuclear Cells
PCR	Polymerase Chain Reaction
PIC	Participant Identification Centre
PSQI	Pittsburgh Sleep Quality Index
RCT	Randomised Controlled Trial
REC	Research Ethics Committee
RPE	Rating of Perceived Exertion
RUH	Royal United Hospital
SAE	Serious Adverse Event
VO_{2MAX}	Maximal oxygen uptake
WHO	World Health Organisation

Trial summary

mai summ	nar y						
Trial Title	Evaluating the safety and acceptability of a progressive exercise training intervention for Chronic Lymphocytic Leukaemia: a randomised-controlled pilot trial.						
Short title	Safety and acceptability of e	exercise for Chronic Lymphocytic Leukaemia.					
Clinical Phase Trial Design Trial Participants	I Pilot, single centre, randomised-controlled, phase I trial People diagnosed with Chronic Lymphocytic Leukaemia (CLL) will be invited to participate in this study. These people will be physically inactive and have asymptomatic early-stage CLL monitored without anti-CLL treatment, also known as 'watch and wait' CLL. Participants will be randomly allocated to either an exercise training intervention group, or a usual care control group.						
Planned Sample Size	Exercise training intervention n= 20 Usual care control group n= 20 Total sample size N= 40						
Intervention Duration	16 weeks						
	Objectives	Outcome Measures					
Primary	Objectives Investigate the safety and acceptability of an exercise training intervention, in physically inactive people, with asymptomatic early stage 'watch and wait' CLL.	 Outcome Measures The following will be assessed for safety and acceptability of exercise: Safety (incidence and severity of adverse events) Uptake (proportion of people approached who attend screening, proportion of people who attend screening that are deemed eligible) Adherence (proportion of exercise sessions prescribed that are actually completed) Compliance (prescribed vs. actual aerobic exercise performed per exercise session) Retention (the proportion of participants who complete follow-up measures) 					

	Investigate the effect of an	The following measurements will be collected
Secondary	exercise training intervention on CLL	to assess the effect of an exercise training intervention in participants with 'watch and

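### Stepwise regression on an open-ended set of marker changes in at most 40 people cannot measure how well markers predict disease activity, and a responder split made on outcome change would be circular

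*Protocol*

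**What the plan says.** Under Statistics and data analysis, the Statistical analysis plan states: "The project may utilise correlation analysis to establish whether any change in disease activity is associated to a number of mechanistic markers". The same sentence goes on to say that "stepwise multiple regression will identify the extent to which a change in the mechanistic markers predict change in disease activity". Subgroup analysis is then offered as an option, with the example "split to high vs. low responders or by presence of mediating variable(s) for further analysis". No definition of a responder is given.

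The candidate markers come from the secondary outcomes under Aims and outcomes. These are listed by family and by example. Immune competency alone covers "phenotypic and functional analyses of PBMCs, differential blood count, viral infection history, immunoglobulins, complement proteins", and further families cover cytokines and metabolic and hormonal factors. Background and Summary groups the proposed mechanisms into four domains: inflammation, metabolic hormones, adipose tissue and immune function.

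On size, the Trial summary gives "Total sample size N= 40", split equally between the arms. The Sample size section expects 20% drop out and says "There is limited information available to enable a formal sample size calculation".

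**The concern.** Stepwise selection searches the candidates for the strongest observed association and then reports that association as if it had been the only one examined. The p-values are too small, the confidence intervals too narrow and R-squared too large. The bias grows with the number of candidates and shrinks with the number of people. Here the candidates are open-ended and the people few. The protocol asks the method to quantify the extent of prediction, which is the quantity that selection distorts most.

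Splitting people into high and low responders raises a second problem. If response means change in the outcome, the groups are formed after randomisation from the result itself. They will differ whether or not anything real separates them.

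At stake are the mechanistic conclusions. Learning how exercise might act on the tumour is a stated rationale in Background and Summary, and the results are to be published.

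**Working it through.** The protocol gives no power-based figure to reproduce. The marker count, entry rule, marker correlation, responder definition, test-retest correlation and arm shifts below are assumptions, shown as ranges.

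**Number of people.** Recruited: 40. With both visits: 40 × (1 − 0.20) = 32. The plan imputes missing values, so the nominal n may be 40; both sizes are used.

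**Chance of at least one false predictor.** Assume entry at p<0.05, removal at p>0.10 and no marker related to the outcome. Something is selected whenever the smallest single-marker p-value is below 0.05. For m independent markers this is 1 − 0.95^m:
- m = 5: 1 − 0.774 = 22.6%
- m = 10: 1 − 0.599 = 40.1%
- m = 20: 1 − 0.358 = 64.2%

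Markers from the same blood sample may be correlated. Simulation (20,000 runs per cell for the selection rate, 1,200 runs of the full stepwise procedure for R-squared) gives:

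| Candidates | Independent | Pairwise correlation 0.3 | Mean apparent R-squared when selected, n = 32 | Same, n = 40 |
|---|---|---|---|---|
| 5 | 23% | 20-21% | 0.19 | 0.15 |
| 10 | 40% | 35% | 0.22 | 0.17 |
| 20 | 64% | 54-55% | 0.27-0.28 | 0.22-0.23 |

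**Hand check on R-squared.** A first marker enters only if its r-squared exceeds t²/(t² + n − 2). At n = 32, t = 2.042: 4.170/34.170 = 0.122. At n = 40, t = 2.024: 4.098/42.098 = 0.097. So the first marker enters only if it appears to explain at least 10-12% of the variance, even when the truth is zero.

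**Responder split, if it is a median split on outcome change.** For 20 people (one arm) and pure noise, the mean gap in change between the halves is 1.53 SD of change. The correlation of change with baseline is −√((1 − r)/2), where r is the test-retest correlation. The expected baseline gap between the halves, in baseline SD, is therefore 1.53 × √((1 − r)/2):
- r = 0.70: 1.53 × 0.387 = 0.59 SD (p<0.05 in about 26% of runs)
- r = 0.90: 1.53 × 0.224 = 0.34 SD (about 11%)
- r = 0.95: 1.53 × 0.158 = 0.24 SD (about 8%)

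**Arm term, if the arms are pooled and arm is left out.** Suppose exercise shifts both a marker and the outcome by d SD, with no link within either arm. The pooled correlation has size (d²/4)/(1 + d²/4):
- d = 0.5: 0.0625/1.0625 = 0.06, false positives about 6%
- d = 0.8: 0.16/1.16 = 0.14, about 12-13%
- d = 1.0: 0.25/1.25 = 0.20, about 20-24%

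The nominal rate is 5%.

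**The case against.** The strongest defence is that this is a pilot. The sentence on correlation and regression opens conditionally, subgroup analysis is optional, and Background and Summary calls the tumour-cell and mechanism work preliminary. A separate analysis plan may exist with a candidate list, covariates and a responder definition. That is fair, and it keeps this from being a major point. It does not rescue the method: the protocol names stepwise selection and says what it will establish, and calling the work preliminary does not correct an inflated R-squared.

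Some stronger readings go beyond the text:
- A reader might infer that the trial is bound to report noise as predictors. With 5 candidates the chance is about one in five, and no marker count is stated.
- A reader might infer that candidates will be as numerous as participants. The lists are open-ended, but nothing gives a number.
- A reader might infer that responders are defined by change in CLL cells. The text does not say so; fitness or adherence would also fit.
- A reader might infer that the models ignore arm and baseline. The text is silent on covariates, and silence is not a decision to leave them out.
- A reader might infer that markers for the next trial will be picked from this output. The protocol says only that the data will show whether a future trial has promise and will inform its sample size.

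**Conclusion.** The point holds for the stated method. Under no true association and entry at p<0.05, stepwise selection reports at least one predictor in about 20-23% of trials with 5 candidates, 35-40% with 10 and 54-64% with 20. The mean apparent R-squared is then about 0.15-0.28. The exact rate depends on a marker count and entry rule that the protocol does not give, and it falls as markers become more correlated. Even so, the method cannot quantify the extent of prediction at this sample size.

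The objections to the responder split and to pooling the arms are conditional. If the split is made on outcome change, it is post-randomisation and circular, with a baseline imbalance whose size depends on test-retest correlation. If arm is left out of pooled models, false associations rise noticeably only when exercise shifts both variables by about 0.8 SD or more.

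This should be corrected, but it concerns secondary, exploratory analyses and leaves the primary safety and acceptability outcomes untouched.

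**What to change.** In the Statistical analysis plan section, replace the stepwise regression with a short list of marker changes named before the data are seen, for example one for each of the four mechanistic domains in Background and Summary. Name the disease-activity measure. For each marker, fit one regression of the Visit 3 measure on marker change, arm and the Visit 2 value of that measure. Report the coefficient with its 95% confidence interval, labelled exploratory. Call it associational too, because marker change arises after randomisation.

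With four independent tests the chance of at least one false finding is 1 − 0.95^4 = 18.5% at 0.05 each, or 1 − 0.9875^4 = 4.9% at 0.0125 each.

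Drop any responder split defined by the outcome, or limit it to labelled description without tests. Examine effect modification only by variables measured at baseline.

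The cost is a change of wording and fewer nominally significant predictors to report. No new data or visits are needed.
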